11. PARTICIPANT RIGHTS AND CONFIDENTIALITY.....	4140

11.1	Institutional Review Board (IRB) Review.....	4140
11.2	Informed Consent Forms	4140
11.3	Participant Confidentiality	4141
11.4	Study Discontinuation.....	4241
12.	COMMITTEES	4241
13.	PUBLICATION OF RESEARCH FINDINGS	4242
14.	REFERENCES.....	4242
	I. Procedures Schedule	
	II. Informed Consent Form Template	
	III. Other (add as many appendices as necessary)	

STUDY TEAM ROSTER

Principal Investigator:

- - [name], P.T., Ph.D.
 - Virginia Commonwealth University; [contact] (T);
[contact]

Study Coordination and Data Collection Team

- [name], B.S. – Study Coordinator
 - [contact](T); [contact]

Other Key Members

- [name]. - Bioengineer
 - Virginia Commonwealth University, [contact] (T);
[contact]

PARTICIPATING STUDY SITES

This is a single site study conducted at Virginia Commonwealth University.

PRÉCIS

A fundamental clinical problem in individuals with chronic low back pain is the significant alteration in movement patterns that restrict lumbar spine motion. This restriction of lumbar motion is particularly evident in patients with kinesiophobia; that is, a fear of movement due to possible injury or reinjury. For chronic back pain patients with kinesiophobia it is critical to develop an effective intervention to increase spine motion while minimizing concerns of pain and harm. Accordingly, we have developed an innovative suite of virtual reality games that track whole-body motion and are designed to encourage spinal flexion while reducing concerns of pain and harm among individuals with low back pain. Our games have two distinct advantages. First, within this game environment we can manipulate the target locations to encourage progressively larger amounts of lumbar spine flexion during game play. Second, virtual reality games are potent distractors that can reduce attention to pain.

We have recently established safety and feasibility when played for 3 consecutive days. In the proposed study participants will complete 18 intervention visits over 9 weeks with the number of sessions tapered across weeks (i.e., 3 sessions/week in weeks 1-3, 2 sessions/week in weeks 4-6, and 1 session/week in weeks 7-9).

Our co-primary outcome variables will be change in pain and change in disability from baseline to 1-week post-treatment (Aim 1). We will also examine changes in expectations of pain/harm and lumbar flexion as potential mechanisms of change in pain and disability (Aim 2). Aim 3 will examine maintenance of treatment gains at 1-, 6-, 12-, 24-, and 48-weeks post-treatment, additional measures of emotional functioning, pain vulnerability, and pain resilience, and real-world activity monitoring

[figure not shown]
(See Recruitment and Pre-Screening – Figure1).

Figure 1

Study Title

VIGOR - Virtual Immersive Gaming to Optimize Recovery in Low Back Pain

Objectives

The co-primary clinical outcomes are changes in pain and disability. Secondary objectives are to examine potential mechanisms of pre- to post-treatment changes in clinical outcomes and maintenance of treatment gains.

Design and Outcomes

VIGOR is a Phase II, double-blind, randomized, placebo-controlled trial to test the efficacy and safety of a novel, immersive, virtual reality intervention on outcomes of pain, disability, pain/harm expectancy, and lumbar flexion in individuals aged 18-60 years of age with chronic low back pain.

Individuals with chronic low back pain will be randomly assigned to play one of two versions of the virtual reality game suite for 9-weeks. In the experimental group, gameplay will promote progressive increases in lumbar flexion. The control group will play the same immersive video games, but the parameters will be modified such that

only small excursions of lumbar flexion are needed to successfully complete gameplay. The co-primary clinical outcomes of changes in pain and disability will be assessed at 1-, 6-, 12-, 24-, and 48-weeks post-treatment. Additionally, individual differences in expected pain, expected harm, and lumbar flexion will be measured at pre-treatment baseline and at each of the follow-up intervals in the laboratory. Finally, participant activity in their natural environment will be monitored for 7 days following each follow-up laboratory visit using accelerometry.

Interventions and Duration

Participants will complete 18 intervention visits over 9 weeks with the number of sessions tapered across weeks (i.e., 3 sessions/week in weeks 1-3, 2 sessions/week in weeks 4-6, and 1 session/week in weeks 7-9).

Sample Size and Population

We will recruit 230 participants with chronic low back pain (CLBP) and fear of movement. We will include participants with CLBP between the ages of 18-60 and who report no health condition(s) that may restrict movement or preclude safe participation. Participants will be recruited from the general population and specific organizations such as Virginia Commonwealth University's Medical Associates.

Aim 1: Power analyses were conducted to determine the sample size needed to achieve clinically important differences in our co-primary clinical outcome measures of pain and disability. Based on the extant literature, we based our analyses on a \geq 30% decrease in pain ratings¹ (on the 0-10 NRS scale) and a 30% decrease in disability ratings on the RMDQ² in the experimental group. Further, we predict a 10% decrease in pain and disability in the control group to account for potential placebo effects. The population standard deviations were set at 75% of the population mean values. The pre-post correlation was estimated as $r=0.7$. These population parameters translate into an effect size of $f=0.30$. Using these parameters, we drew 10,000 samples from a normal population distribution. Based on these parameters, to achieve power of 80% and $\alpha=0.05$ will require a total $N=78$.

Aim 2 & 3: Power analyses were conducted to determine the sample size needed to address hypotheses 2.1, 2.2, and 3. Using the method described by Morris (2008),³ we calculated effect size estimates from randomized clinical trials on the effects of graded activity or graded exposure interventions on changes in disability among individuals with CLBP.⁴⁻⁷ For our power analyses, we adopted the median estimated effect size: $\delta = .45$, which corresponds to what would commonly be described as a medium effect size. Following Raudenbush and Liu's (2000) recommendation,⁸ we set the residual error variance to 1 and estimated the between-subject slope variance to be 0.30. For power equal to .80 and $\alpha=0.05$, a sample size of 209 participants was indicated.

Based on the sample size calculations, using a sex-stratified random allocation table, we need a minimum sample of 209 participants to address Aims 1-3. To allow for 10% attrition from baseline to 48-week follow-up, we will recruit 230 participants.

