2. BACKGROUND AND RATIONALE

2.1 Background on Condition, Disease, or Other Primary Study Focus

Low back pain is the second most common reason for a visit to a physician, with direct medical costs exceeding \$90 billion per year in the United States alone.^{9, 10} These costs are driven primarily by 7-10% of patients who develop chronic low back pain (CLBP) that can last for many years.⁹⁻¹¹ Fear of movement (i.e., kinesiophobia) due to expectations of pain and harm is an important risk indicator for the development of persistent pain and disability, with studies consistently showing that high fear is one of the strongest predictors of the transition from sub-acute to CLBP.¹²⁻¹⁵ Specifically, fear encourages the adoption of maladaptive movement patterns wherein tasks of daily living are performed with reduced lumbar spine flexion and compensatory increases of knee, hip, and shoulder flexion. Using our standardized reaching tasks, we have repeatedly demonstrated reduced lumbar spine flexion in fearful acute, sub-acute, and CLBP sufferers.¹⁶⁻²⁰ While avoidance of lumbar flexion may benefit these CLBP sufferers in the short-term by reducing their fear of injury, in the long-term, limited lumbar flexion becomes an entrenched pattern that can lead to shortening of spinal peri-articular connective tissues, changes in surrounding muscles,²¹⁻²³ and increased risk for chronicity.

The current standard of care for individuals with high fear and CLBP is graded exposure therapy, which promotes gradual confrontation of avoided movements in order to reduce expectations of pain/harm.²⁴ Although recent RCTs with CLBP patients indicate that this approach significantly reduces fear of movement, it has not led to greater reductions in disability when compared to standard therapy.^{4, 6} We posit that prior studies have not seen the full benefit of this approach because they have failed to make restoration of lumbar flexion an explicit focus of therapy. Without this goal, patients are able to complete the graded movement tasks using maladaptive movement patterns that can impede full recovery. Therefore, we hypothesize that explicit efforts to increase lumbar flexion are required to benefit those with CLBP who are typically viewed as having intractable pain and disability.²⁵

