2.2.4 Mechanisms Underlying Proposed Game Intervention

Both Graded Activity (GA) and Graded Exposure (GE) are common approaches to the treatment of CLBP. Graded activity focuses on restoring function regardless of pain. The intervention begins with provision of a treatment rationale emphasizing the negative effects of inactivity and the positive effects of physical activity on well-being, and then uses a combination of activity quotas and positive reinforcement to promote increased activity over time. In contrast, GE focuses on reducing fear of pain and expectations of harm upon movement. Treatment begins with provision of a treatment rationale emphasizing the role of fear as an impediment to functional restoration, and then proceeds with development of an individualized hierarchy of feared movements to guide subsequent sessions of graded exposure. Systematic exposure to feared movement provides repeated opportunities to confront and correct patient misperceptions of the expected relationship between movement and risk of harm. RCTs have shown that both GA and GE produce significant reductions in pain and disability, and that these intervention effects do not differ significantly at post-treatment and 1-, 6-, and 15-month follow-up intervals.^{4, 6, 42} However, a systematic literature review concluded that GA is no more effective than other forms of exercise and that GE is no better than wait-list or usual care controls.⁴³ We hypothesize that GA and GE approaches to CLBP fail to outperform other forms of exercise or usual-care controls because patients can complete the prescribed tasks with restricted lumbar spine motion simply by increasing motion at the ankles, knees, and hips. Indeed, continued restriction of lumbar spine motion may be a key impediment to optimal restoration of function as we have consistently demonstrated that pain-related fear is associated with restricted lumbar flexion among: 1) individuals with subacute LBP,^{16, 35} 2) individuals with CLBP,¹⁸ 3) asymptomatic individuals who have recently recovered from LBP,³⁴ and 4) healthy individuals with experimentally-induced back pain.¹⁹ To address the ubiquitous and persistent problem of restriction of lumbar spine flexion among those with pain-related fear, we specifically designed a suite of virtual reality games (i.e. VR Dodgeball) that necessitate progressively larger excursions of the lumbar spine to successfully complete the games. Similar to GA, we believe that our intervention does not require an explicit focus on psychological factors related to avoidance behavior, but rather operates through a combination of acute distraction from pain, repeated reinforcement of movement goals with feedback of progress, and graded increases in expectations of spinal lumbar flexion across sessions. In a Phase I trial, we demonstrated that individuals with CLBP and pain-related fear who played virtual dodgeball had significant increases spinal motion across sessions. They also rated the game as highly enjoyable and had no adverse outcomes. With sufficient exposure to this intervention, we posit that individuals with CLBP and pain-related fear will develop an implicit understanding that lumbar spine motion is not dangerous and will generalize the unrestricted lumbar spine motion that is promoted by the

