9.2 Sample Size and Randomization

We will recruit 230 participants with chronic low back pain (CLBP) and fear of movement. We will include participants with CLBP between the ages of 18-60 and who report no health condition(s) that may restrict movement or preclude safe participation. Participants will be recruited from the general population and specific

organizations such as Virginia Commonwealth University's University Medical Associates.

Aim 1: Power analyses were conducted to determine the sample size needed to achieve clinically important differences in our co-primary clinical outcome measures of pain and disability. Based on the extant literature, we based our analyses on a \geq 30% decrease in pain ratings¹ (on the 0-10 NRS scale) and a 30% decrease in disability ratings on the RMDQ² in the experimental group. Further, we predict a 10% decrease in pain and disability in the control group to account for potential placebo effects. The population standard deviations were set at 75% of the population mean values. The pre-post correlation was estimated as $r=0.7$. These population parameters translate into an effect size of $f=0.30$. Using these parameters, we drew 10,000 samples from a normal population distribution. Based on these parameters, to achieve power of 80% and $\alpha=0.05$ will require a total $N=78$.

Aim 2 & 3: Power analyses were conducted to determine the sample size needed to address hypotheses 2.1, 2.2, and 3. Using the method described by Morris (2008),³ we calculated effect size estimates from randomized clinical trials on the effects of graded activity or graded exposure interventions on changes in disability among individuals with CLBP.⁴⁻⁷ For our power analyses, we adopted the median estimated effect size: $\delta = .45$, which corresponds to what would commonly be described as a medium effect size. Following Raudenbush and Liu's (2000) recommendation,⁸ we set the residual error variance to 1 and estimated the between-subject slope variance to be 0.30. For power equal to .80 and $\alpha=0.05$, a sample size of 209 participants was indicated.

Based on the sample size calculations, using a sex-stratified random allocation table, we need a minimum sample of 209 participants to address Aims 1-3. To allow for 10% attrition from baseline to 48-week follow-up, we will recruit 230 participants.

Treatment Assignment Procedures

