To address aims 2 & 3 we will build and test linear mixed-effects models for each of the outcome variables. For hypotheses 2.1 and 3, pain, disability, pain/harm expectancy, and lumbar flexion will be the outcome variables, while time (linear and quadratic), treatment group, and the interactions of time and treatment group will be the primary predictor variables. For hypothesis 2.2, pain/harm expectancy and lumbar flexion will serve as the outcome variables, while time (linear and quadratic), treatment group, the time-by-group interactions, pain, and disability will be predictor variables. For hypothesis 3, planned comparisons will be conducted to compare the control and experimental groups at each time period for pain, disability, and activity levels in the natural environment. As noted above, covariates will be added to analyses as needed. The significance level for every omnibus test will be set to 0.05, while Holms procedure will be used to control familywise type-I error rate for post-tests at .05.

Checking Assumptions: Assumptions of LME models will be checked by conducting analyses of model residuals. Violations of normality will be addressed by transforming the data, while outliers or influential cases will be handled by conducting sensitivity analyses. In contrast to the standard repeated measures analyses of variance, with their rigid assumptions about the error covariance structure, LME models permit numerous alternative error covariance structures. This allows for modeling of data that exhibit both heteroscedasticity and autocorrelation, which is likely to characterize the data collected for this study.

Additional Analyses: We will use the same analytic framework to analyze additional measures of core outcome domains, including emotional functioning (e.g., CES-D, POMS-2, PROMIS measures), pain vulnerability (TSK, PCS), pain resilience (PRS, PSEQ), and patient global impression of change (PGIC).

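### The Aim 1 inputs do not give the stated f=0.30 or N=78, and they leave the primary Treatment by Time test at about 70-75% power with 209 participants, although 209 is said to be enough for Aims 1-3

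*Combined protocol and SAP*

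**What the plan says.** The same paragraphs appear in the Précis (Sample Size and Population) and in Section 9.2.

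- **Aim 1.** Pain and disability are assumed to fall by 30% in the experimental arm (at least 30% for pain). For the other arm, "we predict a 10% decrease in pain and disability in the control group to account for potential placebo effects". The SD is 75% of the mean and the pre-post correlation is 0.7. The plan says that these inputs amount to f=0.30, and that 80% power at alpha 0.05 needs a total of 78.
- **Aims 2 and 3.** For Hypotheses 2.1, 2.2 and 3, "we calculated effect size estimates from randomized clinical trials on the effects of graded activity or graded exposure interventions on changes in disability". The choice from these is given as "For our power analyses, we adopted the median estimated effect size", namely .45, and it is used with residual variance 1 and between-subject slope variance 0.30: "For power equal to .80 and $\alpha=0.05$, a sample size of 209 participants was indicated".
- **Conclusion drawn.** 209 is presented as the minimum for all three aims, and recruitment is set at 230 to allow for 10% attrition.

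Sections 1.1 and 9.6 test Hypothesis 1 by the Treatment by Time interaction from baseline to post-treatment. On alpha, Section 9.6 says "The significance level for every omnibus test will be set to 0.05".

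**The concern.** Aim 1 describes its expected effect in two ways that should agree: as raw inputs (30% against 10%, SD, correlation) and as f=0.30. For two equal arms f=0.30 means d=0.60. The raw inputs look much smaller than that, and also smaller than the .45 in the next paragraph. If the raw inputs are what the investigators expect, then 78 is far too few for the primary test, and 209 does not give the co-primary outcomes 80% power. A non-significant primary result would then be judged against a power claim that the plan's own assumptions do not deliver.

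**Working it through.** **Inputs.** Aim 1: 30% and 10% falls, SD 0.75 of the mean, r=0.7, f=0.30, N=78. Aims 2 and 3: delta=.45, residual variance 1, slope variance 0.30, N=209. Both: power 0.80, alpha 0.05. The power paragraphs do not state sidedness, allocation ratio or number of occasions. I assume two-sided tests and 1:1 allocation.

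**1. Reproducing 209.** Take a two-arm comparison of linear slopes with delta in slope-SD units:

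noncentrality = delta × sqrt(tau/(tau+V)) × sqrt(N)/2, with tau=0.30 and V = 1/Σ(t−t̄)².

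Five equally spaced occasions give V=1/10=0.10 and tau/(tau+V)=0.75. Then 0.45 × 0.866 × sqrt(209)/2 = 2.817, and the noncentral t gives 80.1% power; the smallest such N is 209. The five occasions are an assumption: four give 261 and six give 187.

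**2. Effect implied by the Aim 1 inputs.** In units of the baseline mean the arm difference is 0.30−0.10=0.20.

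- Baseline SD: 0.20/0.75 = 0.267.
- Change SD, constant SD: 0.75 × sqrt(2×(1−0.7)) = 0.581; 0.20/0.581 = 0.344.
- Change SD, with SD staying at 75% of each mean: post-treatment SDs are 0.75×0.70=0.525 and 0.75×0.90=0.675. The change SDs are sqrt(0.75²+0.525²−2×0.7×0.75×0.525)=0.536 and, likewise, 0.556. Pooled this is 0.546; 0.20/0.546 = 0.366.
- Baseline-adjusted, constant SD: 0.20/(0.75 × sqrt(1−0.7²)) = 0.373.

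With f=d/2 for two equal arms, f is 0.133, 0.172, 0.183 and 0.187. None is near 0.30.

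**3. Power of the Aim 1 test.** With baseline and one post-treatment visit, the Treatment by Time interaction is the comparison of mean change between arms. Noncentrality is d × sqrt(N)/2, with N−2 degrees of freedom.

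| Standardiser | d | Power, N=78 | Power, N=209 | N for 80% |
|---|---|---|---|---|
| Baseline SD | 0.267 | 21% | 48% | 444 |
| Change SD, constant | 0.344 | 32% | 70% | 267 |
| Change SD, 75% of each mean | 0.366 | 36% | 75% | 236 |
| Baseline-adjusted | 0.373 | 37% | 77% | 228 |

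Simulating the change-score test agrees: 33% and 36% at N=78, and 70% and 75% at N=208. The change-score rows match the planned test; the baseline-SD row is a lower bound.

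**4. Where 78 may come from.** A between-group main effect over two measurements with f=0.30 and r=0.7 has noncentrality N×f²×2/(1+r). At N=77 this is 77×0.09×2/1.7=8.15, which gives 80% power. That is close to 78, but it is a test of the arm average over both visits, not of the interaction. The plan does not say that this test was used, so this is only a possible explanation.

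**5. Sensitivity of the 209 calculation.** Putting the Aim 1 effects in place of delta in step 1 gives 38% (0.267), 57% (0.344) and 63% (0.366) at N=209. This holds only if those effects are on the scale of delta.

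**The case against.** The strongest reply is that the plan's stated Aim 1 effect is f=0.30, or d=0.60, which is larger than .45. At that effect 209 gives 96% power by the slope formula and 99% as a comparison of two means, so the trial would be generously sized. That is correct as far as it goes. But f=0.30 is presented as a consequence of the raw inputs, and it is not one. Either the inputs or f must change, and the documents do not say which was intended. For pain the 30% fall is also a floor, so a larger effect is allowed; for disability it is not.

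A reader might infer that power for Hypotheses 2.1, 2.2 and 3 is really 38-63%. The documents do not support that. Delta sits beside a slope variance of 0.30, while the Aim 1 effects are pre-post mean differences. Converting one to the other needs a baseline variance and a time scaling that the plan does not give. Aim 1 also predicts nothing about expectancy, lumbar flexion or activity, which 209 also serves. The range is a conditional sensitivity result for pain and disability, no more.

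A reader might also infer that the background contradicts .45. Section 2.1, citing two of the four source trials, says of graded exposure that "it has not led to greater reductions in disability when compared to standard therapy". Section 2.2.4 reports a review concluding that "GA is no more effective than other forms of exercise and that GE is no better than wait-list or usual care controls". These leave .45 unjustified for a comparison with an active version of the same game. They do not refute it: non-significant comparisons can coexist with a non-zero median, the other two source trials are not described, and Sections 2.2.4 and 3 also report significant reductions in disability. Whether .45 is a between-arm or a within-arm figure, and against what comparator, cannot be settled from the documents.

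**Conclusion.** The point holds for Aim 1. Its inputs imply d of 0.27 to 0.37, not the 0.60 that f=0.30 represents, and all of these values are below .45. For each co-primary outcome the Treatment by Time test then has about 32-36% power at N=78 rather than 80%, and about 70-75% at N=209. The claim that 209 is enough for Aims 1-3 at 80% power is therefore unsupported for Aim 1 on the plan's own inputs. The shortfall at 209 is moderate: 236 to 267 analysed participants would reach 80% with the change SD.

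This rests on two-sided 5% tests, equal allocation and no covariate gain; baseline adjustment raises power at 209 to about 77%. For Aims 2 and 3 the 209 is arithmetically sound at delta=.45 under the five-occasion assumption. What is missing there is a justification of .45, not a correct calculation.

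**What to change.** Keep recruitment at 230. In the Précis and in Section 9.2:

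1. Correct f=0.30 and N=78 to match the Aim 1 inputs, or correct the inputs if f=0.30 was intended, and name the test that was powered.
2. State that 209 analysed participants give 80% power for Aims 2 and 3 only at delta=.45 on the slope scale used, and give the number and spacing of occasions.
3. State the power of the Aim 1 Treatment by Time contrast at 209 under 30% against 10%: about 70-75% with the change-score SD.
4. List the estimates behind the median of .45 with their comparators, so that its relevance to an active control can be judged.

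The cost is a rewrite of the same paragraphs in two places and a less favourable stated power for the primary aim. No extra patients or data are needed.
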